6.1.4 Clinical Laboratory Tests

Blood and urine samples will be collected at the time points indicated in the SOE ([Appendix 13.1](#)). Hematology, coagulation and serum chemistry assessments will be

performed by the sponsor's central laboratory; urinalysis assessment will be performed locally.

The following hematology, coagulation, serum chemistry, and urinalysis assessments will be performed:

Hematology: Hematocrit, hemoglobin, mean corpuscular hemoglobin, mean corpuscular hemoglobin concentration, mean corpuscular volume, platelet count, red blood cell count, and total and differential (absolute and percent) leukocyte count

Coagulation International normalized ratio, partial thromboplastin time, and prothrombin time

Serum Chemistry: Albumin, alanine aminotransferase, alkaline phosphatase, amylase, anion gap, aspartate aminotransferase, bicarbonate, bilirubin (total and direct), blood urea nitrogen, calcium, chloride, cholesterol (total, high-density lipoprotein, and low-density lipoprotein), creatine phosphokinase, creatinine, gamma-glutamyltransferase, globulin, glucose, lactate dehydrogenase, magnesium, phosphorus, potassium, sodium, total protein, triglycerides, and uric acid

Urinalysis: Appearance, bilirubin, color, glucose, ketones, leukocyte esterase, microscopy (performed if dipstick is positive; includes bacteria, casts, crystals, epithelial cells, red blood cells, and white blood cells), nitrites, occult blood, pH, protein, specific gravity, turbidity, and urobilinogen

Abnormal clinical laboratory values will be flagged as either high or low (or normal or abnormal) based on the reference ranges for each laboratory parameter. The investigator will determine whether any of the abnormally high or low results are clinically significant or not clinically significant. Clinical significance is defined as any variation in results that has medical relevance and may result in an alteration in medical care (e.g., active observation, diagnostic measures, or therapeutic measures). If a clinically significant change from the screening value is noted, the clinically significant value and reason for clinical significance will be documented on the AE page of the eCRF. The investigator will continue to monitor the patient with additional assessments until the value has reached the reference range, or the

value at the Screening Period visit, or until the investigator determines that follow-up is no longer medically necessary.

Liver enzymes/LFTs will be assessed in accordance with the guidelines presented in the US Food and Drug Administration (FDA) Guidance for Industry—Drug-Induced Liver Injury: Premarketing Clinical Evaluation (July 2009).

6.1.5 Adverse Events

6.1.5.1 Definitions of Adverse Events

The investigator is responsible for reporting all TEAEs that are observed or reported during the study, regardless of their relationship to the investigational product or their clinical significance.

An AE is defined as any untoward medical occurrence in a patient enrolled into this study regardless of its causal relationship to the investigational product. The patient's legal representative (parent[s]/caregiver[s]) will be instructed to contact the investigator at any time if any symptoms develop.

A TEAE is defined as any event not present before exposure to the investigational product or any event already present that worsens in either intensity or frequency after exposure to the investigational product.

6.1.5.2 Serious Adverse Events

An SAE is defined as any event that results in death, is immediately life threatening, requires inpatient hospitalization or prolongation of existing hospitalization, results in persistent or significant disability/incapacity, or is a congenital anomaly/birth defect. Important medical events that may not result in death, be life threatening, or require hospitalization may be considered SAEs when, based upon appropriate medical judgment, they may jeopardize the patient or may require medical or surgical intervention to prevent one of the outcomes listed in this definition. Examples of such medical events include allergic bronchospasm requiring intensive treatment in an emergency room or at home, blood dyscrasias or doubling of seizure frequency compared to baseline over a period of 7 days or longer.

6.1.5.3 Eliciting and Documenting Adverse Events

Adverse events will be assessed from the time the patient's legal representative (parent[s]/caregiver[s]) signs the ICF until and including the Follow-Up visit, 14 days after the last dose of the investigational product.

Serious AEs that occur more than 14 days after the last dose of the investigational product need not be reported unless the investigator considers them related to the investigational product.

At every study visit, the patient's legal representative (parent[s]/caregiver[s]) will be asked a standard nonleading question to elicit any medically-related changes in the patient's well-being. They will also be asked if the patient has been hospitalized, had any accidents, taken any new medications, or changed concomitant medication regimens (both prescription and OTC medications).

In addition to patient observations, AEs identified from any study data (e.g., laboratory values, physical examination findings, and ECG changes) or identified from review of other documents (e.g., seizure diaries) that are relevant to patient safety will be documented on the AE page in the eCRF.

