The investigator will also contact the parent/caregiver by telephone on Day 12, or Day 13 or Day 14 to review seizure counts and to assess the patient's status using the above questions.

Patients will return to the study clinic on Day 7 (Visit 3 [\pm 2 days]). Starting from the PM dose on the day of Visit 3, the dose will be escalated and patients will receive the investigational product at a dose of 9 mg/kg orally twice daily. Starting on Day 15, the dose will be escalated again and patients will receive the investigational product at a dose of 15 mg/kg orally twice daily until the end of Treatment Period 1.

At Visit 2 and each visit thereafter, a record of the incidence and severity of TEAEs and SAEs will be collected and this will serve as a primary outcome criterion for this study. Other safety-related parameters such as 12-lead electrocardiogram (ECG), hematology, chemistry, physical examination, and vital signs will also be assessed at specified visits. Seizure diaries will be collected to assess spasms count prior to each visit following Visit 1.

Video-EEG will be repeated at Day 28 (Visit 5 [\pm 2 days]) (overnight video-EEG), following Treatment Period 1 for the assessment of spasms and hypsarrhythmia.

[figure not shown]
At Visit 2 and each visit thereafter, Clinical Global Impression of Change (CGI-C) will be collected from both the investigator and the parent/caregiver.

Treatment Period 2: Dose Tapering Period (Days 29 to 42):

The full dose of the investigational product will be continued until Day 28. At the start of the Dose Tapering Period on Day 29, the dose will be reduced by half. On Day 35, the dose will be reduced by half again, and on Day 42, the investigational product will be stopped. Patients will return to the study clinic on Day 42 (Visit 6 [\pm 5 days]). Refer to [Appendix 13.1](#) for list of tests/procedures.

Follow-Up Period (Day 43 to 56):

Patients will return to the study clinic on Day 56 (Visit 7 [\pm 5 days]). Refer to Appendix 13.1 for list of tests/procedures.

Figure 3-1 Study Design**3.1.1 Rationale of Study Design**

This open-label, multicenter study design allows the investigational product to be given as either add-on therapy or monotherapy. The design and choice of study population for this Phase 2 clinical study is based on the need to provide initial safety, tolerability, PK, and efficacy outcomes of the investigational product for future clinical studies.

4 Patient Selection and Withdrawal Criteria

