6.1.5.7 Assessment of Causality

The investigator's assessment of an AE's relationship to the investigational product is part of the documentation process, but it is not a factor in determining what is or is not reported in the study. If there is any doubt as to whether a clinical observation is an AE, the event should be reported.

The relationship or association of the investigational product in causing or contributing to the AE will be characterized using the following classification and criteria:

Unrelated: This relationship suggests that there is no association between the investigational product and the reported event.

Possible: This relationship suggests that treatment with the investigational product caused or contributed to the AE, i.e., the event follows a reasonable temporal sequence from the time of drug administration or follows a known response pattern to the investigational product but could also have been produced by other factors.

Probable: This relationship suggests that a reasonable temporal sequence of the event with drug administration exists and, based upon the known pharmacological action of the drug, known or previously reported adverse reactions to the drug or class of drugs, or judgment based on the investigator's clinical experience, the association of the event with the investigational product seems likely. The event disappears or decreases on cessation or reduction of the dose of investigational product.

Definite: This relationship suggests that a definite causal relationship exists between drug administration and the AE, and other conditions (concurrent illness, progression/expression of disease state, or concurrent medication reaction) do not appear to explain the event. The event reappears or worsens if the investigational product is re-administered.

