### **3.8 Evaluation of Treatment Safety**

#### **3.8.1 Adverse Events**

An AE is defined as any untoward medical occurrence in a patient enrolled into this study regardless of its causal relationship to the investigational product. The patient's legal representative (parent[s]/caregiver[s]) will be instructed to contact the investigator at any time if any symptoms develop.

A TEAE is defined as any event not present before exposure to the investigational product or any event already present that worsens in either intensity or frequency after exposure to the investigational product.

All AEs will be reported or observed during the study will be recorded on the AE form in the eCRF. The AE and SAE reporting period begins after administration of study drug through the follow up visit. The Investigator will follow-up on all AEs observed or reported by the subject up to the end of the reporting period unless the event stabilizes and follow-up is no longer necessary. The Investigator will follow-up on SAEs until they are considered resolved or the outcome is known.

The following details will be collected for AEs: description of the AE, onset date/time, action taken with study drug (dose not changed, drug interrupted, drug withdrawn, dose increased, not applicable, or unknown), date/time of resolution, any additional treatment given, outcome

(recovered/resolved, not recovered/not resolved, recovered/resolved with sequelae, recovering/resolving, fatal or unknown), severity (mild, moderate, severe), seriousness (yes, no), relationship to study drug (unrelated, possibly, probably, definitely related or unknown), and whether the AE causes early termination of the subject.

The severity of AEs will be categorized as follows:

- Mild: These events require minimal or no treatment and do not interfere with the patient's daily activities.
- Moderate: An AE that is sufficiently discomforting to interfere with normal activities.
- Severe: These events interrupt a patient's usual daily activity and may require systemic drug therapy or other treatment. Severe events are usually incapacitating.

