## 7.12 Analysis of Safety Data

### 7.12.1 Adverse Events

All AEs will be coded to SOC and PT using Medical Dictionary for Regulatory Activities (Version 22.0 or later) and presented by subject in data listings.

A treatment-emergent adverse event (TEAE) is defined as any AE that began or worsened following the start of dosing of Treatment Period 1, Day 1 to Follow-Up.

A treatment-related AE is defined as any TEAE that is assessed by the Investigator as possibly, probably or definitely related to study drug.

Adverse event analyses will be conducted using the Safety Population.

The overall incidence of TEAEs (number and percentage of subjects) as well as the number of events will be summarized for mild TEAEs, moderate TEAEs, severe TEAEs, TEAEs assessed as at least possibly related, SAEs, TEAEs leading to study or drug discontinuation, SAEs related to study drug, life-threatening SAEs and SAEs resulting in death. All AE reports will also include the action taken as a result of the AE such as dose not changed, drug interrupted, drug withdrawn, dose increased, not applicable, or unknown.

The following TEAEs summaries will be presented (where applicable the number of patients (%)) and number of events will be summarized) by SOC and PT for overall treatment group:

- TEAEs
- Treatment-related TEAEs
- TEAEs leading to investigational product discontinuation
- Treatment-related TEAEs leading to investigational product discontinuation
- Serious TEAEs
- Treatment-related serious TEAEs
- TEAEs leading to death
- Treatment-related TEAEs leading to death.

All TEAEs will be summarized by SOC and PT using frequency counts and percentages (i.e., number and percentage of patients with an event); also the number of events will be presented

Tabulations will include an overall incidence of subjects reporting at least one AE, an overall incidence of TEAEs, and incidence within SOC and PT. Each patient may only contribute once (i.e., most severe occurrence) to each of the incidence rates, regardless of the number of occurrences.

For the incidence at the subject level by SOC, PT and relationship to study drug; if a subject experiences more than 1 event within the same SOC and PT, only the most related occurrence (in

descending order of definitely related, probably related, and possibly related) will be included in the incidence.

Listings of AEs, TEAEs, SAEs, TEAEs leading to death and TEAEs leading to study drug discontinuation will also be presented.

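### Protocol 6.1.5.3 waives unrelated SAEs once 14 days have passed since the last dose, but AE collection and the TEAE window run to a Follow-Up visit that can fall 5 to 6 days beyond that point in completers

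*Protocol*

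**What the plan says.** Protocol 6.1.5.3 sets the end of AE assessment as "until and including the Follow-Up visit, 14 days after the last dose of the investigational product", so it names a visit and an interval as if they were the same day. Its next sentence says "Serious AEs that occur more than 14 days after the last dose of the investigational product need not be reported". The only exception it makes is for events judged to be related.

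The visit is not fixed at 14 days. Protocol 3.1 stops dosing on Day 42 and says "Patients will return to the study clinic on Day 56", with a window of ± 5 days; Table 13-1 shows the same window.

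Other sections set no causality condition:

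- Protocol 6.1.5.1: "The investigator is responsible for reporting all TEAEs that are observed or reported during the study, regardless of their relationship to the investigational product".
- Protocol 6.1.5.4: every AE seen or reported during the study goes on the AE page of the eCRF.
- Protocol 6.1.5.5: any AE meeting the SAE criteria is reported within 24 hours.
- Protocol 6.1.5.7, on the causality assessment: "it is not a factor in determining what is or is not reported in the study".
- SAP 3.8.1: "The AE and SAE reporting period begins after administration of study drug through the follow up visit".
- SAP 7.12.1 defines a TEAE as "any AE that began or worsened following the start of dosing of Treatment Period 1, Day 1 to Follow-Up".

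Protocol 11.3 places the Follow-Up visit inside the study. SAP Section 1 calls the SAP consistent with the protocol and SAP Section 4 declares no changes, so neither document resolves the difference.

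**The concern.** When Visit 7 falls later than 14 days after the last dose, there is a stretch in which a non-serious AE must be collected but an unrelated hospitalisation or death may be left out under one sentence of the protocol. Relaxing the duty for serious events only is unlikely to be intended.

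The incidence of TEAEs is the primary endpoint of an open-label, single-arm trial. If a site applies the sentence as written, an unblinded opinion on causality decides whether a late serious event reaches Table 14.3.1.6 (serious TEAEs) or Table 14.3.1.8 (TEAEs leading to death). Related events would be kept and unrelated ones could be lost, which would lower the serious-TEAE count and raise the related share of it. The same cases could be missing from the serious TEAEs and deaths that the DSMB reviews under Protocol 6.4.

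**Working it through.** **Inputs.** Dosing stops on Day 42 (Protocol 3.1); the text allows a last dose on Day 41 or Day 42, so both are used. Visit 7 is Day 56 ± 5, that is Days 51 to 61 (Protocol 3.1, Table 13-1). The SAE limit is 14 days after the last dose (Protocol 6.1.5.3).

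**The plan's own figure.** Day 56 − Day 42 = 14 days, so the stated interval is reproduced for a Day 42 last dose with Visit 7 on its nominal day. With a Day 41 last dose it is 56 − 41 = 15 days. The stated overall duration also checks: 28 + 28 + 14 + 14 = 84 days.

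**Formula.** Gap = max(0, Visit 7 day − (last-dose day + 14)). It counts the days inside the AE and TEAE window on which the 14-day sentence waives unrelated SAEs.

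| Last dose | 14-day limit | Visit 7 | Days since last dose | Gap |
|---|---|---|---|---|
| Day 42 | Day 56 | Day 51 | 9 | 0 |
| Day 42 | Day 56 | Day 56 | 14 | 0 |
| Day 42 | Day 56 | Day 61 | 19 | 5 (Days 57–61) |
| Day 41 | Day 55 | Day 51 | 10 | 0 |
| Day 41 | Day 55 | Day 56 | 15 | 1 |
| Day 41 | Day 55 | Day 61 | 20 | 6 (Days 56–61) |

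**Average size in completers.** Assume Visit 7 is spread evenly over its 11 allowed days and the last dose is on Day 42. Then 5/11 = 45% of completers have some gap, and the mean gap is (1 + 2 + 3 + 4 + 5)/11 = 1.4 days, or 1.4/56 = about 2.4% of a 56-day course.

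**If the last dose moves with the Visit 6 window (assumption).** For a Day 37 last dose and Visit 7 on Day 61 the gap is 61 − 51 = 10 days. For a Day 47 last dose it is 0.

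**Early discontinuers.** Protocol 4.2.2 sends them to the Visit 6 assessments, and Table 13-1 labels that column as the early termination visit. Neither says whether they attend Visit 7, so the end of their AE window is not defined. As an illustration only, a last dose on Day 14 with Visit 7 on Days 56 to 61 would give 56 − 28 = 28 to 61 − 28 = 33 days.

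**Events.** The documents give no SAE rate. As a scale check only, assume a constant hazard, a 56-day risk r of an unrelated SAE between 5% and 30%, and the full 5-day gap for all 35 patients. The risk per patient in the gap is 1 − (1 − r)^(5/56), which is 0.0046 to 0.0313. The expected number of patients is then 35 × 0.0046 = 0.16 to 35 × 0.0313 = 1.1. Under those risks this is a ceiling for a Day 42 last dose, because most Visit 7 dates give a shorter gap or none.

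**The case against.** A reader might infer that late serious TEAEs and deaths enter the tables only if judged related, and that serious-TEAE incidence is therefore biased downwards. The documents do not support that. The sentence is permissive and forbids no report. Protocol 6.1.5.1, 6.1.5.4 and 6.1.5.5 and SAP 3.8.1 all still require the event up to Follow-Up, and at every visit, Visit 7 included, 6.1.5.3 has the parent asked about hospitalisation. Omission is possible, not certain, and any bias depends on it.

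The sentence can also be read more kindly. The one before it equates Follow-Up with 14 days after the last dose, so the waiver may have been meant only for the time after Follow-Up. There it conflicts with nothing, since TEAEs stop at Follow-Up.

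A gap of several weeks in patients who stop early is also tempting to claim. It would need such a patient to attend Visit 7 on the original calendar, which the protocol does not say. The difference between 35 enrolled and 26 completers does not count such patients either.

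Finally, seriousness is not severity: a non-serious AE can be severe, so it is not accurate to say that severe events are dropped and mild ones kept.

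All of this stands, and it limits the consequence. It does not remove the contradiction. The visit window makes the two dates differ, and the 14-day sentence is the only one in the protocol written specifically for late SAEs, so a site could reasonably take it as the exception that governs.

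**Conclusion.** The point holds as an unresolved contradiction over a short window. For completers the gap is 0 days on the nominal schedule with a Day 42 last dose, and at most 5 days (Day 42) or 6 days (Day 41) when Visit 7 is on Day 61. This assumes dosing ends as scheduled. For early discontinuers the gap is undefined.

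In that window a stated rule, applied as written, can remove unrelated serious TEAEs and deaths from the safety tables and keep related ones. The number of events affected cannot be derived. The overall TEAE incidence is well protected: SAP 7.12.1 counts each patient once, so an omitted late SAE changes it only for a patient with no earlier TEAE. The exposure lies in the serious-TEAE and death tables, where a single case matters in a trial of about 35 patients.

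**What to change.** In Protocol 6.1.5.3, state that all AEs and SAEs, regardless of relationship, are reported through the actual Follow-Up visit or 14 days after the last dose, whichever is later, and that SAE reporting is limited to related events only after that point. State how this end date applies to patients who discontinue early, including which contact closes their collection. Use the same end date in SAP 3.8.1 and in the TEAE definition in SAP 7.12.1.

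Tying the date to the actual Follow-Up visit alone would be enough to remove the contradiction. Taking the later of the two dates also covers a Visit 7 on Days 51 to 55, which comes before 14 days have passed since a Day 42 last dose (9 days in the earliest case).

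The cost is a few sentences across the two documents, a few more SAE reports, and a brief contact with the family when Visit 7 falls before the 14 days are up.

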6.1.5.4 Reporting Adverse Events

All AEs reported or observed during the study will be recorded on the AE page in the eCRF. Information to be collected includes drug treatment, dose, event term, time of onset, investigator-specified assessment of severity and relationship to the investigational product, time of resolution of the event, seriousness, any required treatment or evaluations, and outcome. Adverse events resulting from concurrent illnesses, reactions to concurrent illnesses, reactions to concurrent medications, or progression of disease states must also be reported. All AEs will be followed to adequate resolution. The Medical Dictionary for Regulatory Activities (MedDRA) will be used to code all AEs.

Any medical condition that is present at the time that the patient is screened but does not deteriorate should not be reported as an AE. However, if it deteriorates at any time during the study, it should be recorded as an AE.

6.1.5.5 Reporting Serious Adverse Events

Any AE that meets SAE criteria ([Section 6.1.5.2](#)) must be reported to Bio-Pharm Solutions Co., Ltd., immediately (i.e., within 24 hours) after the time that the study site personnel first learns about the event. The following contact information is to be used for SAE reporting:

ICON Pharmacovigilance and Safety Services

[REDACTED]

[REDACTED]

